6.2 Treatment Period

Visits 3, 4 and 5 (Treatment visits at Weeks 2, 4 and 6)

Subjects will be required to return to the clinic at weeks 2, 4 and 6 of treatment to perform the following procedures and tests:

- Dose modification to target dose at week 2 and lowering of dose per direction of physician at weeks 4 and 6.
- Blood glucose, creatinine and potassium levels.
- Women of child bearing potential will have a urine pregnancy test to verify they are not pregnant.
- Blood pressure measurement and reading of recording on the blood pressure monitor.
- Review of daily diaries for any side effects.
- Collect and assess study medication; dispense study medication.

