5.2 Dosage and Administration

Entresto will be given orally at the recommended starting dose of 49/51 mg twice-daily. The dose of Entresto should be doubled after 2 to 4 weeks to the target maintenance dose of 97/103 mg twice daily, as tolerated by the patient ^{25,60}.

12 Weeks of Treatment

We will follow the recommended dosages as reported in the Entresto prescribing information sheet distributed by: Novartis Pharmaceuticals Corporation East Hanover, New Jersey 07936. Subjects will initiate with the recommended dose of 49/51 mg (sacubitril/valsartan) twice daily for two weeks. For

Table 1. Criteria to lower dosage or discontinuation of Entresto
1. Hypotension (symptomatic hypotension or orthostatic hypotension, or hypotension that requires treatment)
2. Renal failure. Increase in creatinine > 50% of baseline value.
3. Hyperkalemia. K ⁺ > 5.2 mEq/L
4. Falls (related to hypotensive episodes)
5. Angioedema
Hypotension = a decrease from baseline in sitting systolic blood pressure (SBP) of ≥ 20 mm Hg and a decrease in sitting SBP to < 90 mm Hg or symptoms.

patients not currently taking an angiotensin-converting enzyme inhibitor (ACEi) or an angiotensin II receptor blocker (ARB) or previously taking a low dose of these agents we will initiate treatment with the lowest dose available (24/26) (sacubitril/valsartan) twice daily. After two weeks of treatment the study physician will progressively increase to the target maintenance dose of 97/103 mg (sacubitril/valsartan). Each participant will receive a package with enough pills containing Entresto/placebo that will last until the following schedule visit. To assure adherence to the treatment,

patients will return all the packages with the empty vials at each study visit. Participating patients will be encouraged to follow their standard health care treatment and lifestyle recommendations prescribed

by their attending physician.

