5.2.1 Dose Adjustment

Dose of Entresto is started at the middle level of 49/51 mg twice-daily and if well tolerated by the patient then dosage is increased to the target maintenance dose described above. If manifestations of side effects of Entresto appear (Table 1), dose can be lowered to the lowest dose of 24/26 mg twice-daily. If at the lowest dose level adverse events continue then patient will be withdrawn from the study. Dose of Entresto will be administered following the recommendation as written in the Entresto prescribing information sheet from Novartis Pharmaceuticals Corporation East Hanover, New Jersey 07936 as revised by the FDA on August, 2015 (Patient information sheet attached). The study physician [name] will be responsible for all dose changes in subjects participating in this study. Specific guidelines on dosage change are detailed below.

Dosage modifications guidelines:

Any patient with a serum potassium > 5.2 mEq/L after randomization requires regular, repeated checks of potassium concentration (beyond that prescribed in the protocol) until it is clear that the potassium concentration is stable and not rising into the range of concern (≥ 5.5 and < 6.0 mEq/L) or potential danger (≥ 6.0 mEq/L).

Corrective action for management of hyperkalemia.

Serum potassium > 5.2 and less than or equal to 5.5 mEq/L

- Confirm potassium concentration in a non-hemolyzed sample.
- Reinforce low potassium diet and restriction of food/drinks with high potassium content (e.g. orange juice, melon, bananas, low-salt substitutes etc.).
- Review medical regimen (including dietary supplements and over-the-counter medications) for agents known to cause hyperkalemia. Consider reduction in dose or discontinuation of these agents:
 - Potassium supplements, e.g., potassium chloride.
 - Salt substitutes.
 - Non-steroidal anti-inflammatory drugs (NSAIDs)
 - Herbal Supplements:
 - For example, Noni juice, alfalfa (*Medicago sativa*), dandelion (*Taraxacum officinale*), horsetail (*Equisetum arvense*), nettle (*Urtica dioica*), milkweed, lily of the valley, Siberian ginseng, hawthorn berries.
- Repeat serum potassium measurement within 3 to 5 days.
- If serum potassium remains > 5.2 and ≤ 5.5 mEq/L, regularly monitor serum potassium levels to ensure stability (suggested once monthly).
- Consider down-titration of study medication, according to study physician medical judgment.

Serum potassium > 5.5 and < 6.0 mEq/L

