6.3 Phone Calls

The PI or Study Coordinator will call subjects every two weeks during the treatment period in order to assess AEs. The phone calls will occur at Week 1, 3, 5 and 7.

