6.4 End of Treatment

Visit 6 (End of treatment visit 1)

At the end of the 12 week treatment period, subjects will be asked to return for testing. Subjects will be asked to return within 24 hours of taking their last study pill. The following tests and procedures will be performed:

- Ankle Brachial Index (ABI)
- GXT will be done to determine pain free and maximal walking distance
- A Walking Impairment Questionnaire (WIQ), a 36-item short-form health survey (SF-36), and Quality of Life Questionnaire (PAD-QOL) will be given
- Body height and weight will be measured using standard anthropometric procedures
- Total body lean and fat mass will be determined
- Blood pressure measurement and reading of recording on the blood pressure monitor.
- Review of daily diaries for any side effects.

- Collect and assess study medication.
- Women of child bearing potential will have a urine pregnancy test to verify they are not pregnant.

Visit 7 (End of treatment visit 2)

Visit 7 will occur within 48 hours of visit 6. At that visit the following tests and procedures will be done:

- 10 hour fasting venous blood sample for measurements of plasma Na⁺, K⁺, glucose, creatinine, NT-proBNP, BNP, serum insulin and also urinary cGMP and creatinine.
- Women of child bearing potential will have a urine pregnancy test to verify they are not pregnant. The 6 minute walk test will be performed in a 20 meter corridor.
- Measure BP three times and the average of those measurements will be recorded.
- fMRI and MRS will be performed in a 7 Tesla/90 cm whole-body actively shielded human scanner.

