6.5 Follow-up Visits

Visits 8 (Follow-up, Week 6 after End of Treatment Visit)

Subjects will return 6 weeks after their treatment has ended to assess if any changes have occurred in pain free walking duration, maximal walking duration during the 6 minute walking test. Subjects will have a Walking Impairment Questionnaire (WIQ) and Quality of Life Questionnaire (PAD-QOL) administered. The presence or absence of adverse events following withdrawal of study drug will be assessed.

Schedule of Events

Schedule of Events								
	Visit 1 Screening	Visit 2 Baseline	Study Visits 3-7					Follow-up Visit 8
Time Point		Day 0	Week 2	Week 4	Week 8	Week 12	Week 12	Week 18
Time estimates	4 hours	4 hours	1 hour	1 hour	1 hour	4 hours	4 hours	45 min
Obtain Consent	x							
Ankle brachial Index	x					x		
Duplex ultrasound ¹	x							
Arterial elasticity	X					X		
Questionnaires	x					x		x
Memory test	X							
Height, weight, lean and fat mass	X					X		
Treadmill test	x					x		x
6 minute walk	x	x					x	x
MRI		x					x	
Blood draw for labs	X	x	x	x	x	x	x	
Urine test		x					x	
Blood pressure ²	x	x	x	x	x	x	x	x
Pregnancy test ³	x	x	X	X	X	X	X	X
Receive drug/placebo		x	x	x	x			
Review blood pressure records and diary			x	x	x	x		

1. Screening visit could be 5 hours long if duplex ultrasound is required, if not it will last 4 hours.
2. Visit should occur within 24 hours of last dose of drug.
3. Blood draw at screening and end of treatment visit 1 are following 10 hour fasting to assess serum: creatinine and K⁺, sodium, glucose, and serum insulin. Study visits at weeks 2, 4 and 6 are also fasting 10 hours prior to blood draw to assess: serum glucose, creatinine and potassium.
4. Duplex ultrasound will be perform only on those patients without a duplex ultrasound for the diagnosis of renal artery stenosis within the last year.
5. NIH toolbox for cognitive function.

6. The treadmill GXT test will be used to determine pain free walking distance, maximal walking distance.
7. Subjects will be instructed to measure and record their blood pressure at home, 3 times daily during the treatment period.
8. For women of childbearing potential.

7. Data Handling and Record Keeping

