11.2 Methods to Minimize Risks

Patients will return to the clinic on weeks 2, 4 and 6 of the treatment period to assess for known adverse events and dosage adjustment if necessary. In addition, the clinical coordinator or the principal investigator will contact the subject by phone every other week to assess presence of adverse events and determine if an additional visit to the clinic is required. Patients will maintain a diary provided by the principal investigator to record blood pressure values and the date and time of the occurrence of known or unexpected adverse reactions. Subjects will be verbally warned and given a handout with a list of medications which are contraindicated or potentially cause an adverse interaction with Entresto. The medications on the list are on the Novartis information sheet on Entresto. The study physician and the PI will highlight these medications and the potential adverse events that can occur.

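### As Sections 6.2 to 6.4 are written, no potassium or creatinine check is scheduled between Week 6 and the end of treatment, listed calls stop at Week 7, and the final sample may be up to 72 hours off drug; the Schedule of Events disagrees

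*Combined protocol and SAP*

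**What the plan says.** **Interim chemistry.** Section 6.2 lists glucose, creatinine and potassium under "Visits 3, 4 and 5 (Treatment visits at Weeks 2, 4 and 6". Section 11.2 agrees: "Patients will return to the clinic on weeks 2, 4 and 6 of the treatment period". Footnote 3 of the Schedule of Events also gives Weeks 2, 4 and 6. The grid above that footnote has columns for Weeks 2, 4 and 8 and none for Week 6.

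**Dose.** Section 6.2 moves patients to target at Week 2 and provides for lowering the dose at Weeks 4 and 6. Section 5.2 is more gradual: "After two weeks of treatment the study physician will progressively increase to the target maintenance dose of 97/103 mg". It starts patients who are not on an ACE inhibitor or ARB at 24/26 mg.

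**Calls.** Sections 6.3 and 11.2 both promise contact every second week, in 6.3 explicitly over the treatment period. Section 6.3 then states: "The phone calls will occur at Week 1, 3, 5 and 7".

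**End of treatment.** For Visit 6, Section 6.4 says: "Subjects will be asked to return within 24 hours of taking their last study pill". Study drug is collected at that visit, and its list contains no blood draw. The chemistry is listed under Visit 7, and "Visit 7 will occur within 48 hours of visit 6". The grid marks a blood draw at both Week 12 visits. Footnote 3 supports a draw at the first of them ("Blood draw at screening and end of treatment visit 1 are following 10 hour fasting to assess serum") and names creatinine and potassium.

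**The concern.** The safety rules in Section 5.2.1 depend on laboratory values: repeat potassium within days above 5.2 mEq/L, consider down-titration, stop at 6.0 mEq/L, and investigate a fall in eGFR of 25% or 40%. Table 2 in Section 11.1 likewise names monitoring of potassium and creatinine as the response to hyperkalemia and renal failure. Without a measurement these rules have nothing to act on. By Section 6.2 the measurements, and the scheduled dose reviews, end halfway through treatment.

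The end-of-treatment sample matters for a related reason. It is the only one that could show what happened in the second half, and Section 6.4 lets it be taken after dosing has stopped. A change that settles quickly off drug could then be understated or missed.

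The conflict also has a practical side. Staff cannot follow both the text and the grid. Because Section 5.2 supplies pills to last until the next visit, Week 6 versus Week 8 also decides how much drug is handed out at Week 4.

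**Working it through.** The plan gives no figure for its longest monitoring gap, so there is none to reproduce. The inputs are the visit weeks and windows in Sections 6.2, 6.3 and 6.4 and in the Schedule of Events.

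**Gaps between scheduled checks, in weeks from Day 0**
- Text (2, 4, 6, 12): 2, 2, 2, 6. The longest is 12 − 6 = 6.
- Grid (2, 4, 8, 12): 2, 2, 4, 4. The longest is 4.
- Text plus Week 9 (2, 4, 6, 9, 12): 2, 2, 2, 3, 3. The longest is 3.

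**Share of target-dose time without a check, by the text.** If target is reached at Week 2 (Section 6.2), 6 of 10 weeks, or 60%. If it is reached at Week 4, 6 of 8 weeks, or 75%; this assumes two doublings from 24/26 mg, two weeks apart. Both figures apply to patients who reach target and stay there.

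**Time off drug at the Visit 7 draw.** At most 24 + 48 = 72 hours. A Visit 6 draw is at most 24 hours after the last pill.

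**Calls.** Every two weeks from Week 1 gives Weeks 1, 3, 5, 7, 9 and 11. Two are unlisted: 2 × 30 patients = 60 calls.

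**What the gap costs in detection.** Assume onset is equally likely at any time in Weeks 4 to 12 (8 weeks) and that a Week 12 sample is taken on drug. For gaps of G weeks within that window:
- mean delay in finding a persisting change = Σ(G²/2) / 8
- share of episodes lasting d weeks that no sample catches = Σ max(0, G − d) / 8

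The documents give no episode durations, so three are shown.

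| Checks at Weeks | Gaps | Longest delay (weeks) | Mean delay (weeks) | Missed, d = 1 | Missed, d = 2 | Missed, d = 4 |
|---|---|---|---|---|---|---|
| 4, 6, 12 (text) | 2, 6 | 6 | (2 + 18)/8 = 2.5 | (1 + 5)/8 = 75% | (0 + 4)/8 = 50% | (0 + 2)/8 = 25% |
| 4, 8, 12 (grid) | 4, 4 | 4 | (8 + 8)/8 = 2.0 | (3 + 3)/8 = 75% | (2 + 2)/8 = 50% | 0% |
| 4, 6, 8, 12 | 2, 2, 4 | 4 | (2 + 2 + 8)/8 = 1.5 | (1 + 1 + 3)/8 = 63% | (0 + 0 + 2)/8 = 25% | 0% |
| 4, 6, 9, 12 | 2, 3, 3 | 3 | (2 + 4.5 + 4.5)/8 = 1.4 | (1 + 2 + 2)/8 = 63% | (0 + 1 + 1)/8 = 25% | 0% |

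Moving Week 6 to Week 8 leaves the missed share of 1-week and 2-week episodes unchanged. Keeping Week 6 and adding a check improves every column.

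**The case against.** The best defense is that the plan lowers this risk in other ways. Section 4.2 excludes potassium above 5.2 mEq/L, eGFR below 30, chronic kidney disease as a cause of hyperkalemia, potassium-sparing diuretics, current ACE inhibitor or ARB use, and renal artery stenosis above 60%. Patients record blood pressure at home three times a day. A call can lead to an extra visit (Section 11.2), a raised potassium triggers repeat tests (Section 5.2.1), and the DSMB is to write safety guidelines before recruitment. All of this stands and makes the risk smaller. None of it supplies a measured value for a patient who was normal at Week 6 and has no symptoms, and the protocol does not say that the DSMB guidelines will add chemistry.

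Some stronger readings are tempting but unsupported.
- A reader might infer that the plan breaks its own monthly standard. The instruction to "regularly monitor serum potassium levels to ensure stability (suggested once monthly" applies only to patients whose potassium stays above 5.2 and up to 5.5 mEq/L on repeat testing. It sets no interval for normal values.
- A reader might infer that every final sample is 72 hours off drug. That is the worst case. It needs both windows used in full and Section 6.4 followed against the grid and footnote 3. Footnote 2 asks for a visit within 24 hours of the last dose, but it is not clearly tied to a particular visit.
- A reader might infer that adopting the grid's Week 8 in place of Week 6 solves the problem. It shortens the longest gap, but for patients who reach target at Week 4 it moves the first check after that from 2 to 4 weeks later.
- A reader might expect centers to diverge. Section 4.1 names one setting, so any divergence would be between staff.

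**Conclusion.** The point holds. Sections 6.2 to 6.4 as written leave Weeks 6 to 12 without scheduled potassium or creatinine, list no calls after Week 7, and allow the end-of-treatment sample to be up to 72 hours off drug. The grid conflicts on the third interim visit, where footnote 3 sides with the text. On the Visit 6 draw, grid and footnote agree against Section 6.4.

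A persisting change without symptoms would be found up to 6 weeks after onset, provided that it is still present when the final sample is taken. How much would settle within 72 hours off drug cannot be judged from the documents. A transient episode could be missed altogether: 50% of 2-week episodes under the uniform-onset assumption for Weeks 4 to 12. That percentage is conditional on an episode occurring and says nothing about how often one would.

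This is a gap in safety monitoring that should be corrected. It does not bear on the walking-test comparison.

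**What to change.** 1. **Interim checks.** Keep the Week 6 check and add one potassium and creatinine check at about Week 9, or at the grid's Week 8. Make Sections 6.2 and 11.2, footnote 3 and the grid agree, and match drug supply to the chosen visits. With Week 9, the longest gap falls from 6 to 3 weeks and missed 2-week episodes from 50% to 25%. With Week 8 added, the longest gap is 4 weeks.
2. **End of treatment.** In Section 6.4, list a potassium and creatinine draw at Visit 6, as the grid and footnote 3 already show. Record hours since the last dose for each end-of-treatment sample.
3. **Calls.** In Section 6.3, add Weeks 9 and 11.

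Cost: about 30 extra blood draws (one for each of 30 patients), with an attendance for each; one draw per patient at Visit 6, which the grid already plans; and 60 calls.

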6.3 Phone Calls

The PI or Study Coordinator will call subjects every two weeks during the treatment period in order to assess AEs. The phone calls will occur at Week 1, 3, 5 and 7.

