At each contact with the subject, the investigator must seek information on adverse events by specific questioning and, as appropriate, by examination. Information on all adverse events should be recorded immediately in the source document, and also in the appropriate adverse event module of the case report form (CRF). All clearly related signs, symptoms, and abnormal diagnostic procedures results should be recorded in the source document, though should be grouped under one diagnosis. A adverse event monitoring form will be use to interview patients during the biweekly phone call to assess presence or absence of adverse events.

All adverse events occurring during the study period must be recorded. The clinical course of each event should be followed until resolution, stabilization, or until it has been determined that the study treatment or participation is not the cause. Serious adverse events will be collected for the six month period following study product administration. Serious adverse events that are still ongoing at the end of the study period must be followed up to determine the final outcome. Any serious adverse event that occurs after the study period and is considered to be possibly related to the study treatment or study participation should be recorded and reported immediately.

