11.1 Potential Risks

As part of the PARADIGM-HF clinical trial adverse reactions occurring at an incidence of $\geq 5\%$ in patients who were treated with ENTRESTO in the double-blind period are shown in Table 2.

Table 2. Adverse effects and percentage of cases in the PARADIGM-HF.

Adverse effects	Entresto	Placebo + Enalapril	Preventive or corrective action
Angioedema, %	0.5	0.2	Discontinue
Hypotension, %	18	12	Dose adjustment of blood pressure lowering medications
Serious hypotension, %	1.5	1.5	Dose adjustment of blood pressure lowering medications
Renal failure, %	5	5	Monitor creat and blood urea
Hyperkalemia	12	14	Monitor K+
Cough, %	9	13	Modify dose
Dizziness, %	6	9	Prevent hypotension
Falls, %	1.90	1.30	Prevent hypotension

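### Section 6.3 requires two-weekly adverse-event calls through 12 weeks of treatment but lists only Weeks 1, 3, 5 and 7, leaving out Weeks 9 and 11

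*Combined protocol and SAP*

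**What the plan says.** Section 6.3 has two sentences. The first sets the rule: "The PI or Study Coordinator will call subjects every two weeks during the treatment period in order to assess AEs". The second sets the dates: "The phone calls will occur at Week 1, 3, 5 and 7".

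The rule appears twice more. The adverse-event recording text (under 9.1.2) says "A adverse event monitoring form will be use to interview patients during the biweekly phone call to assess presence or absence of adverse events". Section 11.2, on minimising risk, has the coordinator or principal investigator contact the patient "by phone every other week to assess presence of adverse events and determine if an additional visit to the clinic is required". Neither gives a week at which calls stop.

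The length of treatment is not in doubt. Section 2.1 randomises patients to 12 weeks, and section 6.4 says "At the end of the 12 week treatment period, subjects will be asked to return for testing".

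Clinic visits during treatment are stated in two ways. Section 6.2 says "Subjects will be required to return to the clinic at weeks 2, 4 and 6 of treatment". Section 11.2 agrees, as does a footnote to the Schedule of Events: "Study visits at weeks 2, 4 and 6 are also fasting 10 hours prior to blood draw". The columns of the Schedule itself show Weeks 2, 4 and 8. The Schedule has no row for phone calls.

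**The concern.** The two sentences of 6.3 cannot both be followed. Staff who apply the rule will call at Weeks 9 and 11; staff who work from the list will stop at Week 7. Section 6.10 counts any noncompliance with the protocol as a deviation, so either practice departs from one of the two sentences.

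The calls have a safety function. Section 11.2 uses them to decide whether a patient needs an extra clinic visit. In the late weeks patients may be taking up to 97/103 mg twice daily (section 5.2), and section 4.2 excludes anyone currently on an ACE inhibitor or ARB. Diaries and home blood pressure readings continue, but the protocol has staff review them only at clinic visits, and none is planned between the third treatment visit and Week 12. Without the two calls, early recognition of a late problem depends on the patient reporting it.

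**Working it through.** **Inputs**

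- Interval between calls: 2 weeks (6.3, first sentence; repeated in the adverse-event recording text and in 11.2).
- First call: Week 1 (6.3, second sentence).
- Treatment length: 12 weeks (2.1 and 6.4).
- Listed calls: Weeks 1, 3, 5, 7 (6.3, second sentence).
- Clinic visits on treatment: Weeks 2, 4, 6 (6.2, 11.2, Schedule footnote) or Weeks 2, 4, 8 (Schedule columns).
- Fixed contacts at either end: Day 0 and Week 12.

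**Step 1: can the list be reproduced from the rule?** Start at Week 1, add 2 repeatedly and stop before Week 12. This gives 1, 3, 5, 7, 9, 11, which is 6 calls. The list has 4. Missing: Weeks 9 and 11, so 2/6 = 33%. The list would be complete for an 8-week treatment period, but the document gives no such period, so that is at most a guess at how the list arose.

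**Step 2: longest interval without planned staff contact.** Merge calls and visits in time order and take the largest difference between neighbours.

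| Calls | Visits | Contact weeks | Longest gap | Share of 12 weeks |
|---|---|---|---|---|
| 1, 3, 5, 7 | 2, 4, 6 | 0, 1, 2, 3, 4, 5, 6, 7, 12 | 12 − 7 = 5 weeks | 5/12 = 42% |
| 1, 3, 5, 7 | 2, 4, 8 | 0, 1, 2, 3, 4, 5, 7, 8, 12 | 12 − 8 = 4 weeks | 4/12 = 33% |
| 1, 3, 5, 7, 9, 11 | 2, 4, 6 | 0, 1, 2, 3, 4, 5, 6, 7, 9, 11, 12 | 11 − 9 = 2 weeks | 2/12 = 17% |
| 1, 3, 5, 7, 9, 11 | 2, 4, 8 | 0, 1, 2, 3, 4, 5, 7, 8, 9, 11, 12 | 11 − 9 = 2 weeks | 2/12 = 17% |

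**Step 3: does any other text reconcile the two sentences?** No section says that calls end or become less frequent after Week 7. The other two statements of the rule are open-ended, and the Schedule is silent on calls.

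**Step 4: could a call pick up anything relevant?** Table 2 in 11.1 gives rates from the heart-failure trial for the drug and for its enalapril comparator: hypotension 18% and 12%, dizziness 6% and 9%, falls 1.9% and 1.3%. A patient can report all three by phone. The figures show only that such events are plausible. They do not estimate how many would occur after Week 7 in patients with PAD.

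**The case against.** The strongest reply is that this is a clerical slip with a clear intention behind it. The two-weekly rule is stated three times and the short list once, so a sensible coordinator would keep calling. Much also continues after Week 7: home blood pressure three times a day, the adverse-event diary, instructions on recognising and reporting events, an emergency card, repeat potassium checks for anyone above 5.2 mEq/L, and a DSMB that receives all adverse events. The listed calls already cover the main titration period, because the move to target dose starts at Week 2 and section 6.2 describes Weeks 4 and 6 as visits for lowering the dose. Nothing shows that the later, steady-dose weeks carry more risk. In Table 2, dizziness was less frequent on the drug than on the comparator. Finally, the fifth week of the 5-week gap comes from the separate conflict over whether the third treatment visit is at Week 6 or Week 8.

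Most of this stands, and it limits the consequence. The rule is probably what was intended, the harm is modest, and only the two missing calls belong to 6.3. It does not remove the contradiction. The list is the only place where call dates are given, so it is what staff are likely to schedule from. Home readings and diaries reach staff at visits, so they do not replace a call in the interval when no visit is planned.

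**Conclusion.** The inconsistency is real and should be corrected. Section 6.3 lists 4 of the 6 calls that its own rule requires. If the list is followed, there is no planned staff contact for the last 5 weeks of treatment, or the last 4 if the Schedule's Week 8 visit is right.

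This rests on two readings: that the treatment period named in 6.3 is the 12 weeks given in 2.1 and 6.4, and that calls start at Week 1 as listed. Whether staff would actually stop at Week 7 is not known.

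The consequence is possible delay in recognising late adverse events. Events in that window are still collected at Visit 6, through questioning, diary review and the monitor readings. The walking-test comparison is unaffected.

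**What to change.** Replace the second sentence of 6.3 with: *Calls are made at Weeks 1, 3, 5, 7, 9 and 11 of treatment.* This works whether the third treatment visit is at Week 6 or Week 8, so it need not wait for that conflict to be settled.

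The cost is one line of text and two more short calls per patient, at most 2 × 30 = 60 in all. Staff who already make these calls would use the existing adverse-event form. A question on missed or stopped capsules could be added to that form, but the correction does not depend on it. The late-treatment interval without laboratory checks is a separate matter that phone calls do not close.
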